APPENDIX D. ACTIVITY SCHEDULE

The following table shows the required activities across the study visits. The individual activities are described in further detail in the Operations Manual.

Study Activities Table

Activity	Screening Period	Treatment Period				Follow-Up Period
	UP to Day -30	Day 1	Day 7 (phone call) (± 2 days)	Day 15 (± 2 days)	Day 29 (± 2 days) or Premature Discontinuation	30-Day Follow-Up (± 7 days)
INTERVIEWS & QUESTIONNAIRES						
Informed consent	✓					
Eligibility criteria	✓	✓				
Medical/surgical history	✓					
Adverse event assessment	✓	✓	✓	✓	✓	✓
Prior/concomitant therapy	✓	✓	✓	✓	✓	✓
Time of last dose of bronchodilator (if applicable)	✓	✓		✓	✓	✓
Date and time of previous 3 doses of study drug				✓	✓	
LOCAL LABS & EXAMS						
Height	✓					
Weight	✓	✓			✓	✓
Vital signs (include oral temperature, respiratory rate, heart rate, and blood pressure)	✓	✓		✓	✓	✓
Pulse oximetry	✓	✓		✓	✓	✓
Physical examination (full)	✓					
Physical examination (limited to throat, chest, heart)		✓		✓	✓	✓
Urine pregnancy test (females of childbearing potential only; to be followed by serum pregnancy test only if urine test is positive)		✓			✓	✓
12-lead ECG (after at least 5 minutes of rest while supine)	✓			✓	✓	
Sweat collection (send sample to central laboratory)	✓	✓		✓	✓	✓
Spirometry (on Days 1 and 15, pre-dose [0 hr] and 3 - 5 hr following dose). Numbers in parentheses indicate the number of tests.	✓	✓ (2)		✓ (2)	✓	✓
CENTRAL LABS						
CFTR Genotyping	✓					

Activity	Screening Period	Treatment Period				Follow-Up Period
	UP to Day -30	Day 1	Day 7 (phone call) (± 2 days)	Day 15 (± 2 days)	Day 29 (± 2 days) or Premature Discontinuation	30-Day Follow-Up (± 7 days)
Urine test for drugs of abuse	✓					
Serology for HBsAg, HCV, HIV-1 and HIV-2 antibodies	✓					
Serum pregnancy test (females of childbearing potential only)	✓					
High-sensitivity C-reactive protein (hsCRP), clinical chemistry, hematology (complete blood count), urinalysis	✓	✓		✓	✓	✓
Follicle-stimulating hormone (FSH) (postmenopausal females ≤ age 55 years only)	✓					
Blood samples for ABBV-3067 and ABBV-2222 pharmacokinetic assay (Day 15 samples pre-dose [0 hour], 2, 4, and 6 hours following dose; Day 29 approx. 24 hours following last dose). Numbers in parentheses indicate the number of samples to be drawn.				✓ (4)	✓ (1)	✓ (1)
Optional biomarker sample: Whole blood		✓			✓	
Rx TREATMENT						
Randomization/drug assignment		✓				
Dispense study drugs		✓		✓		
Perform drug reconciliation				✓	✓	
Study drug administered at site after a meal		✓		✓		

APPENDIX E. PROTOCOL SUMMARY OF CHANGES

Previous Protocol Versions

Protocol	Date
Version 1.0	02 May 2019
Version 2.0	28 August 2019

The purpose of this version is to make the following changes:

Modified rescreening language regarding SwCl test in Section 4.2. **Rationale:** SwCl test does not need to be repeated during rescreening as disease diagnosis biomarker.

Added eligibility criteria to specify the requirements for subjects from Study M19-771 in Section 5.1. **Rationale:** Subjects participated in Study M19-771 are allowed to participate in Study M19-530 as long as they meet the eligibility criteria.

Added Montelukast to prohibited medication list in Section 5.3. **Rationale:** Montelukast is a CYP2C8 substrate, and is a commonly used medication in CF patients.

2 PROTOCOL ACTIVITIES BY VISIT

2.1 Individual Treatment Period Visit Activities

This section presents a list of activities performed during each visit, organized by visit. The dot pattern on the upper right indicates the place of the visit in the overall Treatment Period Activity Schedule.

Activities are grouped by category (Interview, Exam, etc.). Further information is provided in Section 3.

SCREENING (Up to Day -30):

 INTERVIEW	
 • Informed consent • Eligibility criteria • Medical/surgical history 	
 • Adverse event (AE) assessment • Prior/concomitant therapy • Time of last dose of bronchodilator (if applicable)
 EXAM	
 • Full physical examination, including height and weight • Vital signs^a • 12-lead electrocardiogram (ECG)^b 	
 • Pulse oximetry^a • Sweat collection • Spirometry
 CENTRAL LAB	
 • Cystic fibrosis transmembrane conductance regulatory (CFTR) genotyping • Serology for hepatitis B virus surface antigen (HBsAg), hepatitis C virus, human immunodeficiency virus (HIV) Type 1 and 2 (HIV-1 and HIV-2) antibodies • High-sensitivity C-reactive protein (hsCRP), clinical chemistry, hematology (complete blood count [CBC]), and urinalysis 	
 • Urine test for drugs of abuse • Serum pregnancy test (for females of childbearing potential) • Follicle-stimulating hormone (FSH) (for postmenopausal females ≤ 55 years of age)

NOTES:

Section 4.1 of the protocol outlines the circumstances for which retesting of individual labs or spirometry may be performed without repeating all screening procedures. If a screen failure occurs for other reasons that may be corrected and the sponsor's study physician or delegate approves rescreening the subject, then CFTR genotyping, SwCl, and FSH (if applicable) do not need to be repeated.

- Vital signs (Includes oral temperature, respiration rate, heart rate, blood pressure) and pulse oximetry after at least 5 minutes of rest.
- After at least 5 minutes of rest while supine.

DAY 1:

 INTERVIEW	
 • Eligibility criteria • AE assessment • Prior/concomitant therapy 	
 • Time of last dose of bronchodilator (if applicable)
 EXAM	
 • Weight • Vital signs^a • Limited physical examination^b 	
 • Pulse oximetry^a • Sweat collection • Spirometry^c
 LAB	
 • Urine pregnancy test 	
 CENTRAL LAB	
 • hsCRP, clinical chemistry, hematology (CBC), and urinalysis • Serum pregnancy test^d 	
 • Optional biomarker sample: whole blood
 TREATMENT	
 • Randomization/drug assignment • Dispense study drug 	
 • Study drug administered at the site after a meal

NOTES:

- a. Vital signs (Includes oral temperature, respiration rate, heart rate, blood pressure) and pulse oximetry after at least 5 minutes of rest.
- b. Includes throat, chest, heart, and symptom-directed exam.
- c. Pre-dose (0 hour) and 3 to 5 hours following dose.
- d. Only for confirmation if urine test is positive.

DAY 7 (Phone call only ± 2 days):

 INTERVIEW	
 • AE assessment • Prior/concomitant therapy
---	--

DAY 15 (± 2 days):

	INTERVIEW	
 • AE assessment • Prior/concomitant therapy 	
 • Collect date and time of previous 3 doses of study drug • Time of last dose of bronchodilator (if applicable)
	EXAM	
 • Vital signs^a • Limited physical examination^b • 12-lead ECG^c 	
 • Pulse oximetry^a • Sweat collection • Spirometry^d
	CENTRAL LAB	
 • hsCRP, clinical chemistry, hematology (CBC), and urinalysis 	
 • Blood samples for ABBV-3067 and ABBV-2222 plasma concentrations assay^e
	TREATMENT	
 • Dispense study drug • Perform drug reconciliation 	
 • Study drug administered at the site after a meal

NOTES:

- a. Vital signs (Includes oral temperature, respiration rate, heart rate, blood pressure, preferably before blood draw) and pulse oximetry after at least 5 minutes of rest.
- b. Includes throat, chest, heart, and symptom-directed exam.
- c. After at least 5 minutes of rest while supine, preferably before blood draw.
- d. Pre-dose (0 hour) and 3 to 5 hours following dose.
- e. Pre-dose (0 hour) and 2, 4, and 6 hours following dose.

DAY 29 (± 2 days) or

PREMATURE DISCONTINUATION:

 INTERVIEW	
 • AE assessment • Prior/concomitant therapy 	
 • Collect date and time of previous 3 doses of study drug • Time of last dose of bronchodilator (if applicable)
 EXAM	
 • Weight • Vital signs^a • Limited physical examination^b • 12-lead ECG^c 	
 • Pulse oximetry^a • Sweat collection • Spirometry
 LAB	
 • Urine pregnancy test (for females of childbearing potential) 	
 CENTRAL LAB	
 • hsCRP, clinical chemistry, hematology (CBC), and urinalysis • Serum pregnancy test^e 	
 • Blood samples for ABBV-3067 and ABBV-2222 plasma concentrations assay^d • Optional biomarker sample: whole blood
 TREATMENT	
 • Perform drug reconciliation 	

NOTES:

- a. Vital signs (Includes oral temperature, respiration rate, heart rate, blood pressure, preferably before blood draw) and pulse oximetry after at least 5 minutes of rest.
- b. Includes throat, chest, heart, and symptom-directed exam.
- c. After at least 5 minutes of rest while supine, preferably before blood draw. If abnormal - clinically significant, it should be repeated at the follow-up visit or earlier.
- d. Approximately 24 hours following last dose.
- e. Only for confirmation if urine test is positive.

2.2 Individual Post-Treatment Period Visit Activities

This section presents a list of activities performed during each visit, organized by visit.

Activities are grouped by category (Interview, Exam, etc.). Further information is presented in Section 3.

30-Day Follow-up Visit (\pm 7 days):

 INTERVIEW	
 • AE assessment • Prior/concomitant therapy 	
 • Time of last dose of bronchodilator (if applicable)
 EXAM	
 • Weight • Vital signs^a • Limited physical examination^b 	
 • Pulse oximetry^a • Sweat collection • Spirometry
 LAB	
 • Urine pregnancy test 	
 CENTRAL LAB	
 • hsCRP, clinical chemistry, hematology (CBC), and urinalysis 	
 • Serum pregnancy test^c • Blood samples for ABBV-3067 and ABBV-2222 plasma concentrations assay

NOTES:

- Vital signs (Includes oral temperature, respiration rate, heart rate, blood pressure) and pulse oximetry after at least 5 minutes of rest.
- Includes throat, chest, heart, and symptom-directed exam.
- For confirmation only if urine test is positive.

3 STUDY PROCEDURES

3.1 Subject Information and Informed Consent

The investigator or his/her representative will explain the nature of the study to the subject and answer all questions regarding this study. Prior to any study-related screening procedures being performed on the subject or any medications being discontinued by the subject in order to participate in this study, the informed consent statement must be reviewed, signed, and dated by the subject or their legally authorized representative, the person who administered the informed consent, and any other signatories according to local requirements. A copy of the signed informed consent will be given to the subject and the original will be placed in the subject's medical record. An entry must also be made in the subject's dated source documents to confirm that informed consent was obtained prior to any study-related procedures and that the subject received a signed copy.

Information regarding benefits for subjects and information regarding provisions for treating and/or compensating subjects who are harmed as a consequence of participation in the study can be found in the informed consent form.

Optional biomarker research samples will only be collected if the subject has voluntarily signed and dated a written consent form describing the research. The written consent may be part of the main consent form. If the subject does not consent to providing optional samples, the subject will still be allowed to participate in the study.

3.2 Medical History

A complete medical history including demographics, medical conditions, surgical history, genotype, medication use, and history of tobacco, cannabis, alcohol, and drug use will be taken at screening. The number of hospitalizations and/or number of episodes of intravenous (IV) antibiotic use for sinopulmonary signs and symptoms (i.e., exacerbations) in the 12 months prior to Screening will be recorded. The subject's medical history will be updated at the Day 1 visit. This updated medical history will serve as the baseline for clinical assessment.

3.3 Drug and Alcohol Screen

Urine specimens will be tested at the screening visit for the presence of drugs of abuse. The panel for drugs of abuse will minimally include the drugs listed below. Any positive result must be assessed for clinical significance. These analyses will be performed by the certified central laboratory chosen for the study.

- Opiates
- Barbiturates
- Amphetamines
- Cocaine
- Benzodiazepines
- Alcohol
- Phencyclidine
- Propoxyphene
- Methadone

3.4 Adverse Event Assessment

Please refer to Section [4.2](#).

3.5 Pharmacokinetic Sampling

Collection of Samples for Analysis

Blood samples for the analysis of ABBV-2222 and ABBV-3067 plasma concentrations will be collected from subjects on the study days and time points specified in Section [2.1](#).

Subjects should be instructed to not to take study drug before coming to the site on the day of the Day 15 and Day 29 visits.

At the Day 15 visit, a trough (predose) pharmacokinetic sample should be collected prior to the administration of study drug. Additional pharmacokinetic samples will be taken 2, 4, and 6 hours following the dose, as outlined in Section 2.1. Subjects should take the dose of study drug within an hour after eating a meal at the study site.

For all pharmacokinetic samples, the date and accurate time of the pharmacokinetic sample collection will be recorded on the lab requisition form.

At the Day 15 and Day 29 visits, the date and time of the previous 3 study drug doses before those visits will be recorded on the electronic case report form (eCRF).

Refer to the study specific laboratory manual for detailed instructions on sample collection, processing, and shipment.

Measurement Method

Plasma concentrations of ABBV-3067 and ABBV-2222 will be determined by the Bioanalysis Department at AbbVie using a validated method.

3.6 Biomarker Sampling

Optional whole blood samples will be collected for biomarker research as specified in Section 2. All biomarker samples should be labeled and shipped as outlined in the study-specific laboratory manual. AbbVie (or people or companies working with AbbVie) will store the samples and data in a secure storage space with adequate measures to protect confidentiality. The samples may be retained while research on ABBV-3067 and ABBV-2222 (or drugs of this class) or cystic fibrosis (CF) and related conditions continues, but for no longer than 20 years after study completion, or per local requirements.

3.7 12-Lead Electrocardiogram

A 12-lead ECG will be performed at the designated study visits as specified in Section 2. The ECG should be performed prior to blood collection and after the subject has been resting supine for at least 5 minutes.

The ECGs will be evaluated by an appropriately trained physician at the site ("local reader"). The local reader from the site will sign and date all ECG tracings and will provide his/her global interpretation as a written comment on the tracing using the following categories:

- Normal ECG
- Abnormal ECG – not clinically significant
- Abnormal ECG – clinically significant

Only the local reader's evaluation of the ECG will be collected and documented in the subject's source folder. The automatic machine reading (i.e., machine-generated measurements and interpretation that are automatically printed on the ECG tracing) will not be collected. If an ECG at the Day 29 visit is interpreted as abnormal – clinically significant, it should be repeated at the follow-up visit or earlier, per the investigator's discretion until satisfactory clinical resolution or stabilization of the finding.

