3.15 Clinical Laboratory Tests

The blood samples for serum chemistry tests will be collected prior to study drug dosing on Day 1 and Day 15. Fasting or non-fasting status will be recorded in the source documents and on the laboratory requisition. The baseline laboratory test results for clinical assessment for a particular test will be defined as the last measurement prior to the initial dose of study drug.

Samples will be obtained for the laboratory tests listed in Table 1 at the time points specified in Section 2.

Table 1. Clinical Laboratory Tests

Hematology ^a	Clinical Chemistry ^a	Other Tests
Hematocrit Hemoglobin Mean Corpuscular volume White blood cell count Neutrophils Lymphocytes Monocytes Eosinophils Reticulocyte count Platelet count (estimate not acceptable) Bands (if present)	hsCRP Blood urea nitrogen Creatinine Total bilirubin Direct and indirect bilirubin Alanine aminotransferase (ALT) Aspartate aminotransferase (AST) Alkaline phosphatase Sodium Potassium Calcium Inorganic phosphorus Total protein Glucose Albumin Chloride Bicarbonate	Urine: ^b drugs of abuse and alcohol Urine ^f and serum human chorionic gonadotropin ^{b,c,d} follicle-stimulating hormone ^{b,c,e} Urinalysis: ^a Specific gravity Ketones pH Protein Glucose Blood Bilirubin Leukoesterase Nitrites Microscopic examination, if indicated
Coagulation^a		Serology^b
Prothrombin time (PT)/INR Activated partial thromboplastin time (aPTT)	Creatinine clearance (Cockcroft-Gault calculation) Gamma-glutamyl transferase (GGT) Uric acid Lactate dehydrogenase Creatine phosphokinase Cholesterol Triglycerides	HBsAg Anti-HCV antibody HIV-1 and HIV-2 antibodies

INR = international normalized ratio, HBsAG = Hepatitis B virus surface antigen, HCV = Hepatitis C virus, HIV = Human immunodeficiency virus, hsCRP = High-sensitivity C-reactive protein

- a. Chemistries, hematology, coagulation and urinalysis labs should be performed at all visits.
- b. Performed only at screening.
- c. Females only.
- d. Pregnancy testing is not required for females of non-childbearing potential.
- e. If needed to determine postmenopausal status.
- f. Local test.

A certified laboratory will be utilized to process and provide results for the clinical laboratory tests. Laboratory reference ranges will be obtained prior to the initiation of the study.

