### **ECG**

ECG is collected at Screening, Day 15 and Day 29 visits. ECG findings will be summarized by treatment group for each visit. Summaries will include n (%) of patients in following categories:

- Normal

- Abnormal - Not Clinically Significant
- Abnormal - Clinically Significant
- Unable to Evaluate
- Missing

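### No ECG is scheduled at a defined post-dose time, so the plan does not assure any recording near peak drug concentration

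*Protocol*

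**What the plan says.** SAP 9.6 gives the visits: "ECG is collected at Screening, Day 15 and Day 29 visits". There is none on Day 1, so two scheduled ECGs fall on treatment.

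Three places deal with how the ECG is taken:

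- Protocol Appendix D gives only a resting condition: "12-lead ECG (after at least 5 minutes of rest while supine".
- Operations Manual 3.7 adds an order: "The ECG should be performed prior to blood collection and after the subject has been resting supine for at least 5 minutes".
- Operations Manual 2.1, note c for both Day 15 and Day 29, softens it: "After at least 5 minutes of rest while supine, preferably before blood draw".

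The surrounding schedule determines what that order means in practice:

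- Subjects are told not to dose at home on the day of either visit (Operations Manual 3.5).
- On Day 15, "At the Day 15 visit, a trough (predose) pharmacokinetic sample should be collected prior to the administration of study drug". All four PK draws are listed in Operations Manual 2.1: "Pre-dose (0 hour) and 2, 4, and 6 hours following dose".
- Operations Manual 3.15 says: "The blood samples for serum chemistry tests will be collected prior to study drug dosing on Day 1 and Day 15".
- On Day 29 nothing is dosed. Treatment ends the day before (Protocol 4.1), and Appendix D times the PK sample as "Day 29 approx. 24 hours following last dose".

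**The concern.** The 12-lead ECG is a named safety endpoint (Protocol 3.3 and 7.4), and Protocol 5.5 lists arrhythmia, conduction abnormality and prolonged QTcF among the reasons for withdrawal. If an effect on rhythm, conduction or repolarisation depends on concentration, it is easiest to see when concentration is high. The plan fixes post-dose times on Day 15 for PK sampling (2, 4 and 6 hours) and for spirometry (3 to 5 hours), but for no ECG.

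Two things are at stake. First, a clean ECG table could be read as reassurance about the whole dosing interval when most or all of the recordings were made at its end. Part 1 safety data feed the choice of ABBV-2222 dose for Part 2, and Part 2 selects the ABBV-3067 dose for later studies. Second, because the order is mandatory in tone in one place and a preference in another, sites may differ. Day 15 ECGs could then mix pre-dose and post-dose recordings. Operations Manual 3.7 has the reader sign and date the tracing but does not ask for a clock time to be collected, so the two kinds could not be separated in the analysis.

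**Working it through.** The plan states no figure on this point, so there is none to reproduce. The check is a comparison of passages, followed by an illustration under assumed values.

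**Step 1. Where each scheduled ECG falls relative to dosing**

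| Visit | Dose taken that day? | Blood draws | Time of ECG implied |
|---|---|---|---|
| Screening | No (before treatment) | Screening laboratory samples | Off treatment |
| Day 15 | Yes, on site | Chemistry and trough PK before the dose; PK at 2, 4 and 6 h after it | Not stated. Pre-dose if the ECG precedes all draws; post-dose if it precedes only a later one |
| Day 29 (completers) | No; last dose the day before | One PK sample about 24 h after the last dose | About 24 h post-dose, whichever of ECG and draw comes first |
| Premature Discontinuation | Dosing already stopped | One PK sample | Time since last dose not fixed; visit preferably within 2 weeks (Protocol 5.6) |

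**Step 2. How firm the Day 15 placement is**

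- Operations Manual 3.7 puts the ECG before blood collection. It does not say which of the Day 15 collections is meant.
- Note c makes the order a preference.
- A site working through the visit in sequence would do the ECG, then chemistry and trough PK, then the dose. That ECG is about 24 hours after the previous day's dose.
- A site that did the ECG just before the 2, 4 or 6 h draw would also be within the wording.

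So the number of ECGs the plan requires at a post-dose time is 0 of 2, and the number it permits is 1 of 2.

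**Step 3. Illustration of what a 24-hour recording might miss**

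The documents shown give neither time of peak nor half-life for either drug. Both are assumed here. With once-daily dosing at steady state and mono-exponential decline from the peak, the share of peak concentration left at 24 h is

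share = 2^−((24 − t_peak) / t_half)

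| Assumed half-life | Peak at 2 h | Peak at 4 h | Peak at 6 h |
|---|---|---|---|
| 6 h | 2^−(22/6) = 0.08 | 2^−(20/6) = 0.10 | 2^−(18/6) = 0.125 |
| 12 h | 2^−(22/12) = 0.28 | 2^−(20/12) = 0.31 | 2^−(18/12) = 0.35 |
| 24 h | 2^−(22/24) = 0.53 | 2^−(20/24) = 0.56 | 2^−(18/24) = 0.59 |
| 48 h | 2^−(22/48) = 0.73 | 2^−(20/48) = 0.75 | 2^−(18/48) = 0.77 |

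The range, 8% to 77% of peak, runs from a serious gap to a modest one. It shows that the answer depends on data the sponsor holds and the documents do not give.

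**The case against.** A reader might infer that both on-treatment ECGs are fixed before the first blood draw and that no subject will have one near peak. The documents do not support that. The word 'first' does not appear, note c is only a preference, and a Day 15 ECG taken before a later draw would comply.

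A reader might also infer that the withdrawal criterion in Protocol 5.5 is left without effect. That is too strong as well. The criterion is not limited to scheduled ECGs, so one prompted by symptoms could trigger it, and an independent committee reviews unblinded safety data.

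Other objections have weight:

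- **Prior data.** Protocol 4.2 reports multiple dosing of ABBV-2222 at up to 600 mg daily as well tolerated, while Operations Manual 6.4 caps it at 300 mg here. No passage names a QT or conduction signal; the adverse event of special interest is rash. This lowers the urgency. It does not show when earlier ECGs were taken, and exposure comparisons are redacted.
- **Unknown pharmacokinetics.** With a long half-life a 24-hour ECG would see most of the peak exposure. This stands, and it is why no size can be claimed.
- **Limited yield.** Operations Manual 3.7 collects the local reader's category and no machine measurements, and SAP 9.6 tabulates categories. Retiming cannot support concentration-QTc modelling. This stands and limits what the change can achieve.
- **Cost.** A clock time may need an eCRF field, and a 4-hour ECG would fall inside the 3 to 5 hour spirometry window. Both points stand, and both are manageable.

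**Conclusion.** The point holds in a limited form. No ECG has a stated post-dose time; Operations Manual 3.7 and note c differ in strength; together with the pre-dose draws they steer the Day 15 ECG to pre-dose; and the Day 29 ECG is about 24 hours post-dose for completers. ECG data near peak concentration are therefore not assured, and the Day 15 data may be a mixture of times that cannot be told apart.

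These statements follow from the documents. The size of the loss does not: 8% to 77% of peak rests on an assumed peak at 2 to 6 hours, an assumed half-life of 6 to 48 hours and mono-exponential decline. The point is worth acting on because the remedy is cheap, not because a cardiac effect has been shown or is expected. The gain would be in detecting clinically significant abnormalities at post-dose exposure.

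**What to change.** - Reconcile Operations Manual 3.7 with Day 15 note c, so that the order and its strength are the same in both, and state the Day 15 ECG time relative to the dose.
- Time the existing Day 15 ECG shortly before one of the already scheduled post-dose PK draws. The sponsor should choose which from its own data on time of peak.
- If that draw coincides with the post-dose spirometry, place the ECG before the spirometry.
- Record the clock time of the ECG.
- Leave the Day 29 ECG as it is; it supplies the recording at about 24 hours.

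The number of ECGs and visits is unchanged, and subjects are already on site through the 6-hour draw on Day 15. The costs are a revised instruction, possibly one eCRF time field, and a Day 15 ECG taken after a meal and later in the day than on Day 29. The placebo arms would have the same timing, so comparison between arms is not disturbed.

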5 STUDY ACTIVITIES

5.1 Eligibility Criteria

Subjects must meet all of the following criteria in order to be included in the study. Anything other than a positive response to the criteria below will result in exclusion from study participation.

Consent

- ✓ 1. Subjects must be able and willing to voluntarily sign and date each informed consent form (ICF), approved by an institutional review board (IRB), prior to the initiation of any Screening or study-specific procedures.
- ✓ 2. Subjects must be able to understand and adhere to protocol requirements, restrictions, and instructions (per investigator's judgment).

Demographic and Laboratory Assessments

- ✓ 3. Males and females 18 years of age or older on the day the ICF is signed.
- ✓ 4. Subjects must weigh ≥ 35 kg at Screening and Day 1
- ✓ 5. Subjects must have no clinically significant laboratory values at Screening that would pose undue risk for the subject or interfere with safety assessments (per the investigator)
- ✓ 6. The following laboratory values must be in the defined range at Screening:
 - Hepatic function tests (aspartate aminotransferase [AST], alanine aminotransferase [ALT], alkaline phosphatase) $< 3 \times$ the upper limit of normal (ULN) and total bilirubin $< 1.5 \times$ ULN.
 - Estimated creatinine clearance ≥ 50 mL/minute using the Cockcroft-Gault equation
 - Hemoglobin ≥ 10 g/dL
 - Negative serology for human immunodeficiency virus (HIV) infection (HIV-1 and/or HIV-2 antibodies), hepatitis B virus infection (hepatitis B virus surface antigen [HBsAg]), and hepatitis C virus infection (anti-HCV antibody)
- ✓ 7. Absence of clinically significant abnormality detected on electrocardiogram (ECG) regarding rate, rhythm, or conduction (e.g., QT interval corrected for heart rate using Fridericia's formula [QTcF] should be < 450 msec for males and < 460 msec for females)

Disease Activity

- ✓ 8. A confirmed clinical diagnosis of CF and homozygous for the F508del CFTR mutation (documented in the subject's medical record or CF patient registry). Subjects may be randomized based on prior documentation of F508del/F508del mutation, but if the genotype determined at Screening from the central laboratory does not confirm study eligibility, the subject must be discontinued from the study. For subjects who participated in Study M19-771, it is acceptable to use the CFTR genotype that the central lab provided in Study M19-771 to establish eligibility.

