5.5 Withdrawal of Subjects and Discontinuation of Study

A subject may voluntarily withdraw or be withdrawn from the study at any time for reasons including, but not limited to, the following:

- life-threatening AE or a serious adverse event (SAE) that places the subject at immediate risk; or maculopapular rash or other clinical manifestation of allergic drug reaction, for which the
-

severity is categorized as Common Terminology Criteria for Adverse Events (CTCAE, version 5.0) Grade 3 or higher

- worsening pulmonary status that, in the opinion of the investigator, is likely to respond to an approved and commercially available CFTR modulator therapy or that requires a significant change to the existing therapeutic regimen
- serious infections (e.g., requiring parenteral antimicrobial therapy and/or hospitalization)
- fungal infection requiring treatment with a triazole antimicrobial (e.g., fluconazole, itraconazole, voriconazole)
- confirmed pregnancy
- arrhythmia or conduction abnormality, including but not limited to prolonged QTcF, where the severity is categorized as CTCAE (version 5.0) Grade 3 or higher (QTc \geq 501 msec on at least 2 separate ECGs [at least 2 minutes apart] obtained within 10 minutes of the initial recording)
- If any of the following hepatic function test criteria is met, study drug must be discontinued immediately, the medical monitor must be notified, and a supplemental hepatic case report form must be completed (see Section 6.1):
 - AST and/or ALT elevations $> 8 \times$ ULN
 - AST and/or ALT elevations $> 5 \times$ ULN for more than 2 weeks
 - AST and/or ALT elevations $> 3 \times$ ULN, with total bilirubin $> 2 \times$ ULN
 - AST and/or ALT elevations $> 3 \times$ ULN, accompanied by clinical signs or symptoms suggestive for hepatic injury (fatigue, nausea, vomiting, right upper quadrant pain or tenderness, fever, rash, and/or eosinophilia [$> 5\%$]).

A thorough investigation of potential etiologies for the elevated transaminases should be conducted (e.g., trauma, acetaminophen use, viral hepatitis, alcohol ingestion), and the subject should be followed closely for clinical progression.

Subjects for whom treatment is discontinued for elevated hepatic function tests should have transaminases and bilirubin levels repeated by the central laboratory within 48 to 72 hours of the initial finding if possible, and then monitored closely until levels normalize or return to Baseline.

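### The protocol cites numeric QTcF/QTc limits, but only a categorical ECG reading reaches the database, so no QTcF change by dose and no count beyond those limits can be produced.

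*Protocol*

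**What the plan says.** **Entry.** Protocol Section 5.1, criterion 7, asks that there be no clinically significant ECG abnormality. As an example it gives "QT interval corrected for heart rate using Fridericia's formula [QTcF] should be < 450 msec for males and < 460 msec for females".

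**Withdrawal.** Among the reasons for which a subject may be withdrawn, Protocol Section 5.5 lists "arrhythmia or conduction abnormality, including but not limited to prolonged QTcF, where the severity is categorized as CTCAE (version 5.0) Grade 3 or higher". The parenthesis that follows sets QTc at or above "501 msec on at least 2 separate ECGs [at least 2 minutes apart] obtained within 10 minutes of the initial recording". The item says QTcF in one place and QTc in the other.

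**Endpoint.** Protocol Section 3.3 and SAP Section 3.4 both list the 12-lead ECG among the safety endpoints.

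**Collection.** Operations Manual Section 3.7 has a site physician sign and date each tracing and write a global reading on it: normal, abnormal but not clinically significant, or abnormal and clinically significant. It then says: "Only the local reader's evaluation of the ECG will be collected and documented in the subject's source folder". The automatic reading is excluded ("machine-generated measurements and interpretation that are automatically printed on the ECG tracing) will not be collected").

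**Analysis.** SAP Section 9.6 says "ECG findings will be summarized by treatment group for each visit", using those three categories plus unable to evaluate and missing. SAP Appendix B sets potentially clinically significant criteria for laboratory values and vital signs, none for ECG.

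**Schedule.** ECGs are done at Screening, Day 15 and Day 29 (Protocol Appendix D). There is none on Day 1.

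**The concern.** Three numeric limits (450, 460 and 501 msec) refer to a variable that never enters the database. Part 1 chooses the ABBV-2222 dose partly on safety, and Part 2 chooses the ABBV-3067 dose. Laboratory values and vital signs get mean change from baseline and numeric outlier criteria (Protocol Section 7.4; SAP Sections 9.3 and 9.4). The ECG gets neither.

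A modest dose-related shift in QTcF would show only if it led local readers to change a global category. With about 189 subjects at about 59 sites (189/59, roughly 3 per site), that call is spread over many readers. Whoever selects the dose would have no mean change, no trend across doses and no count above a limit.

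**Working it through.** The documents state no QT sample size, power or precision, so there is no figure of the plan's to reproduce on this point. The check has two parts.

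**1. Following the ECG data from rule to table**

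| Step | Source | Interval value needed or produced? |
|---|---|---|
| Entry example | Protocol 5.1, criterion 7 | Needed: 450 and 460 msec |
| Withdrawal item | Protocol 5.5 | Needed: 501 msec, on at least two ECGs |
| Collection | Operations Manual 3.7 | None |
| Summary | SAP 9.6 | None |
| Outlier criteria | SAP Appendix B | None for ECG |

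Three limits need an interval, no interval variable is collected, and no interval analysis is planned. Neither a mean QTcF change nor a count beyond a limit can be computed from what is collected.

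**2. What numeric capture would give**

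Inputs:
- Arm sizes (Protocol Section 4.1): 18 or 9 per active arm and 18 on placebo in Part 1; 18 in the larger Part 2 arms. Pooled placebo is 18 + 9 = 27; SAP Section 9.1 also presents combined placebo for safety.
- SD of QTcF change: **not in the documents**. Assumed 10 to 20 msec.

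Formula for the difference from placebo: 95% half-width = t(0.975, n1 + n2 − 2) × SD × √(1/n1 + 1/n2).

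- 18 v 18: 2.032 × SD × 0.333 = 6.8 msec at SD 10, 13.5 at SD 20
- 9 v 18: 2.060 × SD × 0.408 = 8.4 and 16.8 msec
- 18 v 27: 2.017 × SD × 0.304 = 6.1 and 12.3 msec

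The within-arm half-width for n = 18, t(0.975, 17) × SD/√18 = 2.110 × SD/4.243, looks tighter at 5.0 to 9.9 msec. It is the wrong basis for a drug effect, because it cannot separate drug from drift since Screening.

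**Timing.** Operations Manual Section 3.7 places the ECG before blood collection; the visit notes in Section 2.1 state this as a preference. The first Day 15 sample is pre-dose. The Day 29 sample is about 24 hours after the last dose, and no dose is taken that morning. If the instruction is followed, both on-treatment ECGs fall near trough.

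**The case against.** A reader might infer that the QTc limits govern entry and withdrawal, that nobody could check whether they were applied, and that the measurements are discarded. The documents do not support that reading.

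- **The limits do not strictly govern.** The entry figures are an example attached to a judgement of clinical significance and are phrased with *should*. The withdrawal item is one of several reasons for which a subject *may* be withdrawn.
- **Checking on site is possible.** The reader signs and annotates the tracing, and that same sheet carries the machine values. Protocol Section 9 provides for site monitoring. The text leaves unclear what is kept besides the reader's evaluation, but it says only that the measurements are not collected, not that tracings are destroyed.
- **A QT-driven withdrawal would reach the database.** A worsening that leads to discontinuation counts as clinically significant and is recorded as an AE (Protocol Section 6.1), graded by CTCAE version 5.0. The primary reason goes on the eCRF (Operations Manual Section 3.16). SAP Sections 9.2.2 to 9.2.4 tabulate Grade 3 or higher events and AEs leading to discontinuation. The DMC also reviews unblinded safety data.

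Other points against pressing this hard also stand. Endpoint, collection and SAP agree with one another, and no QT objective is stated. Rash is the only specific risk described in Protocol Section 2.2 as published. Whether QT was characterised earlier depends on Investigator's Brochures that are not available here. No section says that a Fridericia value is printed on the tracing. The recorded values would be near trough, from unstandardised site machines, with a single Screening ECG up to 30 days before Day 1 as baseline.

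What survives is narrower. AE reports give individual cases that a site recognised. They give no estimate by dose, no count against the limits and no msec values.

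**Conclusion.** The point holds as a gap in data capture. From the trial database, QTcF change by arm and the number of subjects beyond the protocol's own limits cannot be obtained, although the ECG is a safety endpoint in a dose-selection trial. This follows from the text alone and rests on no assumed figure.

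The gain from closing the gap is moderate. Against placebo, an 18-subject arm would be estimated to within about 6.8 to 13.5 msec and a 9-subject Part 1 arm to within 8.4 to 16.8 msec, conditional on the assumed SD of 10 to 20 msec. Such data could show a signal. They could not exclude an effect at peak concentration. The change is worth making because it is cheap; its absence does not invalidate the trial's safety assessment.

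**What to change.** **Operations Manual Section 3.7 and eCRF.** Record QT, heart rate, PR and QRS from the existing Screening, Day 15 and Day 29 tracings. Derive QTcF centrally as QT divided by the cube root of RR, with RR = 60/heart rate in seconds, so that nothing depends on which correction a machine prints. Keep the local reader's category. No new ECG and no central reader are needed.

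**SAP Section 9.6.** Add one table:
- mean QTcF change from Screening to Day 15 and Day 29 by arm, with 95% CI;
- difference from placebo with 95% CI (combined placebo for Part 2);
- counts beyond the limits already in the protocol, as description only. A single scheduled reading at or above 501 msec does not by itself meet the Section 5.5 item, which needs at least two ECGs. Either label the count so, or also record the repeat tracings.

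**State the limits in the SAP.** On-treatment ECGs fall near trough, baseline is one Screening ECG, and site-machine values are noisy. The table can show a signal but cannot exclude an effect at peak concentration.

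**Protocol Section 5.5.** Reconcile QTcF and QTc within the withdrawal item. The count against 501 msec depends on which is meant.

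**Cost.** Four fields at three ECGs is 12 values per subject, at most 12 × 189 = 2,268 entries, plus one table. For subjects already past these visits, capture depends on the tracings having been kept.
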